## 5.0 METHODOLOGY

### 5.1 Entry Criteria

#### 5.1.1 Diagnosis/Condition for Entry into the Trial

1. Relapsed and refractory acute myeloid leukemia (**Cohort 1**) – This cohort has enrolled the expected 40 patients and is now completed.
2. Newly diagnosed acute myeloid leukemia in older patients ( $\geq 65$  years) not candidates for intensive induction chemotherapy (**Cohort 2**) – This cohort is closed to new accrual as of 1/8/2020 based on risk benefit analysis information received from the FDA on 1/3/2020.

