### 8.2.2 Sample Size

The primary objective of this study is to estimate the complete response (CR/CRi) rate in each cohort. We estimated sample sizes for the 2 cohorts using a one-sample, one-sided binomial test, with Type I and Type II errors of 0.05 and 0.2, respectively. For Cohort 1, the null and expected response rates were taken to be 0.1 and 0.25, respectively. For Cohort 2, the null and expected response rates were taken to be 0.17 and 0.34, respectively. The sample sizes were calculated to be 38 (which will be rounded to 40) and 40 for Cohorts 1 and 2, respectively.

We used an efficient and flexible design based on Bayesian predictive probability (Lee and Liu, 2008). This design controls the type I and type II error rates and also allows flexible monitoring for futility and efficacy of the new treatment. Furthermore, this design also has better sampling properties than Simon's 2-stage design, i.e. probabilities of early termination for futility under the null hypothesis and for efficacy under the alternate hypothesis are higher and the expected sample size is lower than Simon's 2-stage design.

The following input parameters were assumed in our design: minimum and maximum number of patients was 10 and 40, respectively. Type I and II errors were 0.1 and 0.2, respectively. For cohort 1, the treatment effect for current standard was 0.1 (i.e., probability of CR/CRi) and expected treatment effect for the new treatment was 0.25. For cohort 2, the treatment effect for current standard was 0.17 and expected treatment effect for the new treatment was 0.34. A beta (0.25, 0.75) distribution was assumed for the prior for the expected effect of the new treatment. This is a weak prior, which has negligible effect on the stopping boundaries.

The stopping boundaries for futility are given in the tables below for cohorts 1 and 2. For example, the first row of Table 1 indicates that we would stop the trial for futility if we see 0 responses (CR/CRi) out of the first 10 patients after 6 cycles of therapy (to be evaluable for futility pts must complete at least 2 cycles of therapy); if the study was not stopped after 10 patients, the next evaluation will be done after 14 patients (2nd row). Study will be stopped for futility if we see 1 response or less for futility. If the study continues, the next evaluation happens after 21 patients (3rd row). Study will be stopped if we see 2 or fewer responses in the first 21 patients.

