### **8.2.2.1 Early stopping guideline for toxicity**

Toxicity will be monitored after every 5 patients for each cohort. If it becomes evident that the proportion of patients being removed from the study for toxicity convincingly exceeds 20%, the study will be halted for a safety consultation. The toxicity stopping rule will hold enrollment if the posterior probability of failure being larger than 0.20 is 70% or higher. The prior for this monitoring rule is  $\text{beta}(0.5, 2)$ . This means that our prior guess at the proportion of failures is 20%, and there is 90% probability that this proportion is between 0.01% and 65.8%. The monitoring rule and operating characteristics are given below.

- Stop if 2 out of 5 patients removed from study:  $\text{Pr}(\text{Risk} > 0.2 | \text{Data}) = 0.77$
- Stop if 3 out of 10 patients removed from study:  $\text{Pr}(\text{Risk} > 0.2 | \text{Data}) = 0.715$

- Stop if 5 out of 15 patients removed from study:  $\text{Pr}(\text{Risk} > 0.2 \mid \text{Data}) = 0.852$
- Stop if 6 out of 20 patients removed from study:  $\text{Pr}(\text{Risk} > 0.2 \mid \text{Data}) = 0.823$
- Stop if 7 out of 25 patients removed from study:  $\text{Pr}(\text{Risk} > 0.2 \mid \text{Data}) = 0.8$
- Stop if 8 out of 30 patients removed from study:  $\text{Pr}(\text{Risk} > 0.2 \mid \text{Data}) = 0.781$
- Stop if 9 out of 35 patients removed from study:  $\text{Pr}(\text{Risk} > 0.2 \mid \text{Data}) = 0.766$
- Stop if 10 out of 40 patients removed from study:  $\text{Pr}(\text{Risk} > 0.2 \mid \text{Data}) = 0.752$

Operating Characteristics of stopping rule for toxicity, based on 5000 simulations:

True Toxicity Rate	Probability of declaring treatment too toxic	Average sample size
5%	2.9%	34.1
10%	11.5%	31.8
15%	28.9%	27.6
20%	51.1%	22.8
25%	73.1%	17.8
30%	86.8%	14.0
35%	95.9%	10.7
40%	98.8%	8.6

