### 8.2.2.2 Early Stopping for Safety

The clinical failure of acute graft versus host disease will be monitored after every 5 patients who had a prior history of alloHSCT. If it becomes evident that the proportion of acute graft versus host disease grade 2-4 is greater than 33% the study would also be held for a safety consultation.

The acute GVHD grade 2-4 stopping rule will hold enrollment if the posterior probability of failure being larger than 0.33 is 70% or higher. The prior for this monitoring rule is beta(1,2). This means that our prior guess at the proportion of failures is 33%, and there is 90% probability that this proportion is between 2.5% and 77.6%. The monitoring rule and operating characteristics are given below.

- Stop if 3 out of 5 patients with gr2-4 aGVHD:  $\text{Pr}(\text{Risk} > 0.33 \mid \text{Data}) = 0.832$
- Stop if 5 out of 10 patients with gr2-4 aGVHD:  $\text{Pr}(\text{Risk} > 0.33 \mid \text{Data}) = 0.829$
- Stop if 7 out of 15 patients with gr2-4 aGVHD:  $\text{Pr}(\text{Risk} > 0.33 \mid \text{Data}) = 0.836$
- Stop if 8 out of 20 patients with gr2-4 aGVHD:  $\text{Pr}(\text{Risk} > 0.33 \mid \text{Data}) = 0.719$
- Stop if 10 out of 25 patients with gr2-4 aGVHD:  $\text{Pr}(\text{Risk} > 0.33 \mid \text{Data}) = 0.746$
- Stop if 12 out of 30 patients with gr2-4 aGVHD:  $\text{Pr}(\text{Risk} > 0.33 \mid \text{Data}) = 0.77$
- Stop if 14 out of 35 patients with gr2-4 aGVHD:  $\text{Pr}(\text{Risk} > 0.33 \mid \text{Data}) = 0.79$
- Stop if 15 out of 40 patients with gr2-4 aGVHD:  $\text{Pr}(\text{Risk} > 0.33 \mid \text{Data}) = 0.709$
- Stop if 17 out of 45 patients with gr2-4 aGVHD:  $\text{Pr}(\text{Risk} > 0.33 \mid \text{Data}) = 0.735$

True acute GVHD grade 2-4 rate	Probability of stopping for excess GVHD grade 2-4	Average Sample Size
10%	1.0%	39.7
15%	3.2%	39.0
20%	9.2%	37.3
25%	22.3%	33.9
30%	40.7%	29.4
35%	62.7%	24.2
40%	80.8%	19.1
45%	92.7%	14.5

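### The toxicity table's average sample sizes fit a maximum of 35, not the 40 that the rule and cohort run to; the GVHD table fits a maximum of 40, but its rule lists a look at 45

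*Combined protocol and SAP*

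**What the plan says.** Section 8.2.2.1: "Toxicity will be monitored after every 5 patients for each cohort". The listed boundaries are 2/5, 3/10, 5/15, 6/20, 7/25, 8/30 and 9/35, ending with "Stop if 10 out of 40 patients removed from study". The action is a pause in accrual: "The toxicity stopping rule will hold enrollment" once the posterior probability that the removal rate exceeds 0.20 reaches 70%, under a beta(0.5, 2) prior. The table is headed "Operating Characteristics of stopping rule for toxicity, based on 5000 simulations" and gives no maximum. Section 8.2.2 sets the cohort size for the efficacy design: "minimum and maximum number of patients was 10 and 40, respectively".

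Section 8.2.2.2: acute GVHD of grade 2-4 "will be monitored after every 5 patients who had a prior history of alloHSCT". The listed boundaries are 3/5, 5/10, 7/15, 8/20, 10/25, 12/30, 14/35 and 15/40, ending with "Stop if 17 out of 45 patients with gr2-4 aGVHD". The threshold is 0.33, again at 70% posterior probability, under a beta(1, 2) prior. The table states neither a maximum nor a number of simulations.

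Both sections introduce the table as belonging to the rule listed with it.

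**The concern.** In both tables the average sample size looks too small for the last listed look. When almost no trial stops, the average must lie close to the maximum. In the toxicity table it is 34.1 with 2.9% stopping, under a rule that runs to 40. In the GVHD table it is 39.7 with 1.0% stopping, under a rule that runs to 45.

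The average is the expected number of patients treated before the rule acts or accrual ends. A reader uses it to judge how much exposure a safety rule allows, and a report may repeat it.

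**Working it through.** **Inputs.** The boundaries, priors, thresholds and printed tables come from sections 8.2.2.1 and 8.2.2.2. The cohort maximum of 40 comes from section 8.2.2.

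**1. Boundaries.** After r events in n patients, the posterior is beta(0.5 + r, 2 + n - r) for toxicity and beta(1 + r, 2 + n - r) for GVHD. All 17 printed posterior probabilities reproduce, for example 0.752 at 10/40 and 0.735 at 17/45. One event fewer falls below 0.70 at every look (highest 0.685). The rules themselves are correct.

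**2. Hand bound.** Average N = sum of n x P(stop at n) + Nmax x P(never stop), so average N is at least Nmax x (1 - P(stop)).

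- Toxicity, 5% row, Nmax 40: 0.971 x 40 = 38.8, against 34.1 printed.
- GVHD, 10% row, Nmax 45: 0.990 x 45 = 44.55, against 39.7 printed.

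Neither printed value is possible at the last listed look.

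**3. Exact recursion.** Events in each block of 5 patients are binomial. At each look, paths at or above the boundary are removed and counted as stopped.

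Toxicity (stopping % / average N):

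| True rate | Printed | Maximum 35 | Maximum 40, look at 40 counted | Maximum 40, look at 40 not counted |
|---|---|---|---|---|
| 5% | 2.9 / 34.1 | 2.8 / 34.2 | 2.8 / 39.0 | 2.8 / 39.0 |
| 10% | 11.5 / 31.8 | 12.0 / 31.7 | 12.1 / 36.1 | 12.0 / 36.1 |
| 15% | 28.9 / 27.6 | 28.5 / 27.7 | 29.2 / 31.3 | 28.5 / 31.3 |
| 20% | 51.1 / 22.8 | 50.6 / 22.8 | 52.7 / 25.3 | 50.6 / 25.3 |
| 25% | 73.1 / 17.8 | 72.2 / 17.9 | 75.2 / 19.3 | 72.2 / 19.3 |
| 30% | 86.8 / 14.0 | 87.6 / 13.7 | 90.0 / 14.4 | 87.6 / 14.4 |
| 35% | 95.9 / 10.7 | 95.6 / 10.6 | 97.0 / 10.9 | 95.6 / 10.9 |
| 40% | 98.8 / 8.6 | 98.8 / 8.5 | 99.3 / 8.6 | 98.8 / 8.6 |

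The printed averages match a maximum of 35 within 0.3 patients. At 40 they are too low by 4.9, 4.3, 3.7 and 2.5 patients at 5%, 10%, 15% and 20%. At 35-40% the two maxima can hardly be told apart. Printed stopping is within 0.9 points when the look at 40 is not counted and within 3.2 points when it is (30%: 90.0 against 86.8).

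GVHD (stopping % / average N):

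| True rate | Printed | Maximum 40 | Maximum 45 |
|---|---|---|---|
| 10% | 1.0 / 39.7 | 1.0 / 39.7 | 1.0 / 44.6 |
| 15% | 3.2 / 39.0 | 3.5 / 38.8 | 3.5 / 43.7 |
| 20% | 9.2 / 37.3 | 9.6 / 37.1 | 9.6 / 41.6 |
| 25% | 22.3 / 33.9 | 21.6 / 34.0 | 21.8 / 38.0 |
| 30% | 40.7 / 29.4 | 40.2 / 29.6 | 41.1 / 32.6 |
| 35% | 62.7 / 24.2 | 62.0 / 24.4 | 63.8 / 26.3 |
| 40% | 80.8 / 19.1 | 80.8 / 19.1 | 82.7 / 20.1 |
| 45% | 92.7 / 14.5 | 92.6 / 14.7 | 93.9 / 15.1 |

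The printed table matches a maximum of 40 within 0.7 points and 0.2 patients in every row.

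**4. Simulation error.** With 5000 runs (stated for toxicity, assumed for GVHD), the standard error of average N is 0.080 for toxicity at 5% with maximum 40, and 0.054 for GVHD at 10% with maximum 45. The printed values lie 4.94/0.080 = 62 and 4.92/0.054 = 91 standard errors too low. Against maxima of 35 and 40, all 16 printed averages lie within 1.8 standard errors.

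**The case against.** **The look at 40 is not a real stop.** The toxicity rule pauses enrolment, and a cohort of 40 has none left to pause, so the simulation may properly have omitted that look. This stands for the stopping column: under that convention the printed probabilities are right to within 0.9 points and need not change. It does not rescue the averages, because a trial that passes the look at 35 goes on to enrol 40.

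**The GVHD table may be right and the look at 45 surplus.** This also stands. No section names 45 as the intended number of post-transplant patients, and each cohort is capped at 40. Section 8.2.2.2 does not confine the rule to one cohort, so a count above 40 is not excluded either. A reader might infer that average N is understated in both tables. For GVHD the documents do not support that; they show only that rule and table disagree.

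**Nothing in conduct depends on it.** True. A reader might infer that the stopping rules are faulty or that patients were less protected than planned. The boundaries and posteriors reproduce, so that does not follow. Enrolment is over as well: for Cohort 1, "This cohort has enrolled the expected 40 patients and is now completed", and section 5.1.1 closes Cohort 2 to accrual as of 8 January 2020.

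**Conclusion.** The point holds as a minor arithmetic correction.

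- **Toxicity:** the average sample size column is wrong for the listed rule and the stated cohort maximum, by up to 4.9 patients (39.0 against 34.1 at a 5% rate). The hand bound proves this without any simulation. The stopping column is acceptable or slightly off (at most 3.2 points), depending on an unstated convention for the look at 40.
- **GVHD:** the table is right for a maximum of 40 and does not describe a rule with a look at 45. Its averages are understated, by up to 4.9 patients, only if 45 is the intended maximum; stopping would then move by at most 1.9 points (40%: 82.7 against 80.8).

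The recomputation assumes independent patients, a constant event rate and looks every 5 patients, as the rules are listed. That the tables were run at maxima of 35 and 40 is inferred from the fit; the documents do not say so.

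**What to change.** In 8.2.2.1, state a maximum of 40 under the table and replace the average sample sizes at 5-40% with 39.0, 36.1, 31.3, 25.3, 19.3, 14.4, 10.9 and 8.6. Say whether reaching the boundary at 40 counts as a stop. If it does not, the printed stopping probabilities can remain, or the exact values 2.8, 12.0, 28.5, 50.6, 72.2, 87.6, 95.6 and 98.8% can be given. If it does, use 2.8, 12.1, 29.2, 52.7, 75.2, 90.0, 97.0 and 99.3%.

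In 8.2.2.2, reconcile rule and table and state the maximum. Either state 40 and remove the look at 45 from the rule that the table describes, leaving the table unchanged, or keep that look and restate both columns from the maximum-45 results above.

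The cost is one recomputed column, possibly a second table, and a line under each. The boundaries through 40, the data and the conduct of the trial are unaffected.

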### 8.2.3 Analysis of Primary Endpoint

The primary objective of this study is to estimate the complete remission (CR/CRI) rate of AZA followed by pembrolizumab in 1) relapsed/refractory AML patients, and 2) older ( $\geq 65$  years) newly diagnosed AML patients not candidates for intensive induction chemotherapy. The CR/CRI rate will be reported with an exact binomial, two-sided, 95% confidence interval, separately by each cohort. We will test for heterogeneity of the treatment effect between cohorts using an interaction test, and if there is no evidence of heterogeneity, we will pool all patients treated at the phase II dose/schedule and estimate the CR/CRI rate with an exact binomial, two-sided, 95% confidence interval.

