## 1.0 TRIAL SUMMARY

Abbreviated Title	Azacitidine and Pembrolizumab for the treatment of relapsed/refractory AML patients and newly diagnosed older ( $\geq 65$ years) AML patients who are not candidates for intensive induction chemotherapy
Trial Phase	Phase II
Clinical Indication	Safety Run In Phase (only Cohort 1): The treatment of relapsed and refractory AML patients with no prior history of allogeneic hematopoietic stem cell transplant (HSCT).  Phase 2: Cohort 1: The treatment of relapsed and refractory AML patients. Cohort 2: The treatment of newly diagnosed AML patients ( $\geq 65$ years) who are not candidates for intensive induction chemotherapy.
Trial Type	Interventional
Type of control	No control arm
Route of administration	Intravenous pembrolizumab; intravenous or subcutaneous azacitidine
Trial Blinding	Open Label
Treatment Groups	Cohort 1: Relapsed/refractory AML patients  Cohort 2: Newly diagnosed older patients ( $\geq 65$ years) who are not candidates for intensive induction chemotherapy
Number of trial subjects	Cohort 1: 10-40  Cohort 2: 10-40
Estimated enrollment period	24 months
Estimated duration of trial	48 months
Duration of Participation	Each subject will participate in the trial from the time the subject signs the Informed Consent Form through the final protocol-specified contact. Each treatment cycle will last 28 days. Bone marrow will be examined after 2 and 6 cycles and every 3-6 months thereafter. Patients who achieved complete remission (CR/CRI) or patients without remission but benefiting from therapy (partial remission [PR], morphologic leukemia-free state [MLFS], hematologic improvement [HI], stable disease [SD]) can continue on study receiving both azacitidine and pembrolizumab as long as they have ongoing clinical benefit without evidence of significant toxicity or disease progression and up to 2 years.
Estimated average length of treatment per patient	Up to 2 years or as long as subjects have ongoing clinical benefit without evidence of disease progression or significant toxicity.

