The primary objective of the run in safety phase would be to determine the safe and tolerable dose/schedule of azacitidine and pembrolizumab in patients with AML. We will perform safety run in phase only in Cohort 1 as Cohort 2 patients would be expected to have a same or better tolerability given that they are not heavily pretreated. Patients who relapse post alloHSCT will be enrolled on the study only if they are at least 3 month after alloHSCT and off all immune suppression for at least 3 weeks and have no evidence of active graft versus host disease (GVHD). These patients are expected to tolerate treatment as well as all other relapsed/refractory patients but will be monitored for any GVHD exacerbation in the course of treatment. The primary objective of this Phase 2 study would be to estimate the CR/CRI rates in two separate cohorts of patients: Cohort 1: relapsed or refractory AML patients. Cohort 2: Newly diagnosed older AML patients ( $\geq 65$  years) who are not candidates for intensive induction chemotherapy. Secondary objectives of the trial are to determine safety, tolerability, and analysis of various efficacy parameters such as overall response rate, disease-free survival, progression-free survival, time to progression, overall survival, and exploration of association between potential biomarkers and clinical activity. These analyses will be performed separately for each patient cohort.

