### **8.2 Statistical Analysis Plan**

#### **8.2.1 Safety Run-In**

Each cohort will be enrolled separately with distinct null hypotheses and statistical plans. Since azacitidine and pembrolizumab have not been tested previously in combination in AML patients, we plan first to start enrollment with Cohort 1 (a safety run-in phase). Recognizing that Cohort 1 may also include patients who relapsed after allogeneic hematopoietic stem cell transplant (alloHSCT) and thus may have differential sensitivity (tolerability, immune-related adverse events [IRAEs]) to this drug combination, we will start enrollment in Cohort 1 to include patients who did not have prior alloHSCT.

The primary objective of the safety run-in is to determine the safety and tolerability of AZA followed by pembrolizumab in relapsed and refractory AML using a 3+3 design. We plan to monitor for DLTs in cycles 1, 2 and 3 as some of immunological side effects associated with pembrolizumab may occur with the delay. The first three patients will be enrolled and receive planned azacitidine and pembrolizumab in cycle 1. If 0 or 1 patient of the first three patients has a DLT (dose limiting toxicity) in cycle 1, we will enroll an additional 3 patients to better assess for toxicities. If less than 2 among first 6 patients experiences DLT in the cycle 1-3, we will open enrollment in Cohort 1 for all relapsed/refractory patients including those with prior history of alloHSCT and will also start to enroll patients in Cohort 2. If  $\geq 2$  of the first 3 patients or  $\geq 2$  of 6 patients have DLTs during cycle 1, we will perform safety (detailed toxicity) review to assess for disease versus treatment-related toxicities. Given that pembrolizumab is given only once in cycle 1 (day 8), we will first dose de-escalate azacitidine as detailed in Section 2.2. However, if the safety data analysis suggests that the toxicities are more likely pembrolizumab related, an alternative approach we may take is to exclude pembrolizumab in cycle 1 and start pembrolizumab dosing in cycle 2 when AML is better controlled but maintain azacitidine dose/schedule as described in Section 2.2. If

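### Section 8.2.3 pools the two cohorts' CR/CRi rates after a non-significant test that has little power to separate the rates the plan itself expects

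*Combined protocol and SAP*

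**What the plan says.** Section 8.2.3 begins with the cohort-specific analysis: "The CR/CRI rate will be reported with an exact binomial, two-sided, 95% confidence interval, separately by each cohort". It then provides for a test of heterogeneity of the treatment effect between cohorts, called an interaction test, and adds: "if there is no evidence of heterogeneity, we will pool all patients treated at the phase II dose/schedule and estimate the CR/CRI rate". The pooled rate also gets an exact 95% interval. No model, test statistic, significance level or sidedness is given.

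The rest of the plan treats the cohorts as separate questions. Section 2.1 states that the phase 2 primary objective "would be to estimate the CR/CRI rates in two separate cohorts of patients", and section 8.2.1 says "Each cohort will be enrolled separately with distinct null hypotheses and statistical plans". Section 8.2.2 sizes Cohort 1 on a null rate of 0.10 and an expected rate of 0.25. For the other cohort it says: "For Cohort 2, the null and expected response rates were taken to be 0.17 and 0.34, respectively".

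Two further statements fix what the test can mean. The Trial Summary (section 1.0) gives the type of control as "No control arm". Section 8.2.2 uses the term treatment effect for the response probability itself; for Cohort 1, "the treatment effect for current standard was 0.1 (i.e., probability of CR/CRi").

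**The concern.** With no control arm, a treatment-by-cohort interaction cannot be estimated. What remains is a comparison of two response rates, one in relapsed/refractory patients and one in newly diagnosed older patients. The plan assumes these rates differ, whether the drug combination works or not. A rule that pools unless the difference reaches significance treats failure to detect a difference as support for a single rate. With about 40 patients per cohort, that failure is the likely result even when the design assumptions are right.

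The resulting figure would sit in the primary-endpoint analysis. It would have no null or target to be read against, because sections 2.1, 3.2 and 8.2.2 set these by cohort. Its expected value would also depend on how many patients each cohort enrolled. Because the test and its level are not fixed in advance, the decision to pool is partly open after the data are seen.

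**Working it through.** **Inputs.** Null and expected rates come from section 8.2.2: 0.10 and 0.25 (Cohort 1), 0.17 and 0.34 (Cohort 2). Cohort 1 has n = 40; section 5.1.1 says "This cohort has enrolled the expected 40 patients and is now completed". Cohort 2 has n = 40 as planned in section 8.2.2. It closed early and its final number is not stated, so smaller values are tried below. Assumptions: a two-sided test at 0.05 or 0.10, and all patients treated at the phase II dose/schedule.

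**1. The plan's own sample sizes.** Let φ(p) = 2·arcsin√p. Then n = [(1.645 + 0.842) / (φ(p₁) − φ(p₀))]².
- Cohort 1: φ(0.25) − φ(0.10) = 1.0472 − 0.6435 = 0.4037, so n = 37.9, rounded up to 38.
- Cohort 2: φ(0.34) − φ(0.17) = 1.2451 − 0.8500 = 0.3951, so n = 39.6, rounded up to 40.

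These match the stated 38 and 40. They size each cohort against its own null; nothing in the plan sizes a comparison between cohorts.

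**2. Probability of pooling at the expected rates.** With b(k; n, p) the binomial probability, power = Σₓ Σᵧ b(x; 40, 0.25)·b(y; 40, 0.34)·1{p-value(x, y) < α}, and P(pool) = 1 − power. Full enumeration gives:

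| Test | Power, α 0.05 | P(pool) | Power, α 0.10 | P(pool) |
|---|---|---|---|---|
| Fisher exact | 9.5% | 90.5% | 16.3% | 83.7% |
| Wald (logit) | 13.8% | 86.2% | 22.4% | 77.6% |
| Score (Pearson) | 13.9% | 86.1% | 23.7% | 76.3% |
| Likelihood ratio | 15.0% | 85.0% | 23.7% | 76.3% |

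A continuity-corrected chi-square gives P(pool) of 90.7% and 84.0%. The overall range is 76% to 91%. Looser levels change this only gradually: pooling still follows in about 70–78% of trials at α 0.15 and 65–73% at α 0.20.

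**3. At the null rates (10% versus 17%, 40 per cohort).** Power is 8.8–15.7% at α 0.05 and 14.7–26.5% at α 0.10.

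**4. Smaller Cohort 2.** For a hypothetical 30, 20 or 10 patients at 25% versus 34%, score and Fisher power together span 7.9–13.1% at α 0.05 and 12.3–21.0% at α 0.10. Early closure does not rescue the test.

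**5. A worked result.** Take 10/40 and 14/40 responders (25% and 35%). The score statistic is z = 0.10 / √(0.30 × 0.70 × 2/40) = 0.10 / 0.1025 = 0.98, p = 0.33 (Fisher p = 0.46). The rule pools to 24/80 = 30.0%, exact 95% CI 20.3–41.3%. The cohort intervals are 12.7–41.2% and 20.6–51.7%. With 10/40 in Cohort 1, pooling at α 0.05 is blocked only if Cohort 2 reaches 19/40 (47.5%, score) or 20/40 (50%, Fisher).

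**6. Scale of the shortfall.** For 80% power at 25% versus 34%, two-sided 0.05, with mean rate 0.295: n = [1.96·√(2 × 0.295 × 0.705) + 0.842·√(0.25 × 0.75 + 0.34 × 0.66)]² / 0.09² ≈ 402 per cohort.

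**7. Dependence on enrolment mix.** The expected pooled rate is (40 × 0.25 + n₂ × 0.34) / (40 + n₂): 29.5% for n₂ = 40, 28.0% for n₂ = 20 and 26.8% for n₂ = 10.

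**The case against.** The strongest defence is that nothing the trial decides depends on this sentence. Cohort estimates are reported first and unconditionally, futility and toxicity rules run by cohort, and the reader would see both cohort rates beside the pooled one. This stands, and it is why the point is a low-severity one.

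Second, the rule is not inert. If one cohort sat at its null and the other at its target (10% versus 34%), power would be about 68–86%, so pooling would follow in only 14–32% of trials. This is correct. The criticism applies to the design's own pairs, both null or both as expected, where the rates differ by 7 and 9 points.

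Third, fixing 40 per cohort ignores futility stopping. Applying the section 8.2.2 boundaries at 25% and 34%, about 18% of trials in each cohort stop early. With the score test, pooling then follows in about 71% (α 0.10) to 82% (α 0.05) of trials. Given that Cohort 1 did reach 40, the figures are about 81% and 91%. The lower end moves by a few points and the conclusion does not change.

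Fourth, the plan does name a kind of test. True; what is missing is the model, statistic, level and sidedness. Finally, the mix effect in step 7 is small (2.7 points) beside the interval width and adds little.

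**Conclusion.** The concern holds, at low severity. With 40 patients per cohort and a two-sided test at 0.05 to 0.10, the rule would pool in roughly 76% to 91% of trials if the plan's expected rates of 25% and 34% were both true. Non-rejection is therefore not a basis for quoting one rate, and the pooled rate has no benchmark or objective in the plan. The level of the test and Cohort 2's final size are assumptions, because the documents state neither; smaller Cohort 2 numbers and levels up to 0.20 still leave pooling the likelier outcome. The cohort-specific primary results and the monitoring rules are unaffected. What is at risk is the interpretation of the added pooled estimate.

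**What to change.** Delete the test-then-pool sentence from section 8.2.3, and read each cohort's CR/CRi rate and exact 95% interval against its own null (10% for Cohort 1, 17% for Cohort 2). If a cross-cohort summary is wanted, give the difference in rates with a confidence interval, or an overall rate that is labelled descriptive, shows the number contributed by each cohort, and does not depend on a test result.

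The cost is one sentence deleted or relabelled. All that is lost is a narrower pooled interval that no stated objective uses.
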